3.4.2 Protocol Deviations

For subjects excluded from the Per Protocol Set, all deviations will be shown in a subject listing by treatment group.

3.5 Demographics and Baseline Characteristics

3.5.1 Demographics

Subject demographics and baseline characteristics will be summarized by treatment group and overall for all subject populations.

Descriptive statistics will be displayed for age, height, weight, and body mass index (BMI).

Age is calculated as (date of informed consent - date of birth + 1) / 365.25 and is truncated to complete years. Height, weight and BMI will be summarized with the data collected at the baseline visit.

Frequencies and percentages will be tabulated for sex, race, ethnicity, age group, childbearing potential, enrollment by study center, and country. To assess potential baseline imbalances, the randomized treatment groups will be compared with respect to demographics at baseline using an analysis of variance model (ANOVA) with treatment group as the only independent variable and using a chi square test of independence for the categorical variables.

3.5.2 Medical and Surgical History

Medical and surgical history will be summarized by body system for each treatment group as well as overall for all subject populations. Body system will be presented in descending order for all subjects.

3.6 Prior and Concomitant Medications

Therapies started and stopped prior to the start of study treatment are referred to as prior therapies. Therapies that started prior to treatment and continued on treatment as well as those that started during treatment are referred to as concomitant therapies. In order to define whether a medication with missing start or stop dates is a concomitant medication, refer to the following additional criteria.

- if both the start and stop dates of a particular medication are missing, that medication will be considered concomitant;
- if the start date of a medication is missing and the stop date of that medication falls on or after the dose date, that medication will be considered concomitant;
- if the start date of a medication is missing and the stop date of the medication is prior to the dose date, that medication is considered *not* concomitant;
- If the start date of a medication is prior to the dose date and the stop date of the medication is missing, that medication is considered concomitant.

Prior and concomitant medications will be coded using WHO Drug Dictionary Enhanced version June 2016 and will be classified by Anatomical Therapeutic Class (ATC) level 4 and preferred term (PT) for the Safety Analysis Set. For the presentation of concomitant medications, the ATC level 4 terms will be sorted alphabetically, and within ATC level 4 term, the PT will be used and presented by decreasing total frequency overall.

Frequencies and percentages of subjects using each concomitant medication will be presented for the Safety Analysis Set overall, and by treatment group.

All medication use will be listed regardless of the timing of the start of the medication.

3.7 Treatment Compliance and Exposure

Subjects will receive 1 kit at Baseline and 1 kit at Day 43 (Interim visit). Each kit will contain a bottle for morning doses and a bottle for evening doses. Each morning bottle will contain 90 capsules and each evening bottle will contain 140 capsules.

3.7.1 Compliance to Study Treatment

Compliance, days on treatment, and total capsules taken will be summarized descriptively by treatment group and presented by subject in a listing.

Total capsules taken will be derived as the total number of capsules dispensed minus the total number of capsules returned minus the total number of capsules not taken and not returned.

Expected days capsules taken will be based on the first and last expected days for taking study medication, using all available dosing information on the eCRF. The calculation formula is (last dose date - first dose date + 1).

Compliance will be calculated using the following method based on the number of capsules taken, as reported in the eCRF. The formula for % Compliance is based on the planned titration schedule, and depends on the duration of Expected days capsules taken, as shown:

Expected Days Capsules Taken	% Compliance (as a function of Expected Days Capsules Taken, DAYS)
1-2 Days	= 100 * Total Number Capsules Taken / DAYS
3-6 Days	= 100 * Total Number Capsules Taken / [((DAYS - 2) * 2) + 2]
7-9 Days	= 100 * Total Number Capsules Taken / [((DAYS - 6) * 3) + 10]
10-13 Days	= 100 * Total Number Capsules Taken / [((DAYS - 9) * 4) + 19]
14 Days to End of Treatment	= 100 * Total Number Capsules Taken / [((DAYS - 13) * 5) + 35]

For example, if a subject was on treatment for 2 days and took one capsule during that time, then % Compliance = $100 * 1/2 = 50\%$. If a subject was on treatment for 21 days and took 60 capsules during that time, then % Compliance = $100 * 60/75 = 80\%$.

3.8 [REDACTED]

[REDACTED]

[REDACTED]

[REDACTED]

[REDACTED]

[figure not shown]
[REDACTED]

[REDACTED]

[REDACTED]

A series of black horizontal bars of varying lengths, each ending in a white 'L' shape, arranged vertically. The bars are positioned at different heights, creating a stepped effect. The white 'L' shape at the end of each bar points towards the right edge of the frame.

3.8.2

[REDACTED]

[REDACTED]

The image consists of a series of horizontal bars of varying lengths and positions. The bars are thick and black, set against a white background. They are arranged in a staggered, overlapping pattern, with some bars appearing to be in front of others. The overall effect is a high-contrast, graphic design-like representation of horizontal lines or bars.

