2.2 STUDY DESIGN

This is a multicenter, Phase 2, randomized, parallel (3 arm), double-blind, placebo-controlled study of OV101 in adult and adolescent subjects with AS to assess safety of OV101. Multiple efficacy endpoints are assessed to identify the most appropriate and sensitive outcome measures for future efficacy studies. The study compares 3 different treatment/dosing schedules (15 mg evening dose only [QD], 15 mg evening dose plus 10 mg morning dose [BID], or placebo) for 12 weeks.

[figure not shown]
Approximately 75 subjects will be enrolled at approximately 15 study centers in the United States of America (USA) and Israel. At the completion of the study, there will be approximately 25 subjects in each of the 3 treatment groups: A) single evening dose, B) morning and evening dose, and C) placebo.

Adults aged 18 to 49 years and adolescents aged 13 to 17 at the time of informed consent with a molecular confirmation of AS are eligible for inclusion.

The study comprises a screening period of up to 4 weeks; a baseline visit for treatment randomization; a 12-week treatment period comprised of a 14-day titration period where treatment doses are progressively increased and a 6-week and 12-week visit for safety and efficacy assessments. The final study visit is for the end of treatment visit procedures followed by a 2-week telephone follow-up period to monitor safety.

All subjects receive a morning dose and an evening dose during the entire duration of treatment. Doses are progressively increased in 5 mg increments (OV101 or Placebo) to a target of 15 mg (3 capsules) in the evening for the OV101 groups and 10 mg (2 capsules) in the morning for the OV101 BID group. This up-titration to the target dose occurs unless this target dose is not tolerated. All subjects receive treatment for a maximum of 12 weeks at their highest tolerated dose. Modifications may be made per investigator judgement on urgent need or medical necessity. If tolerability is not acceptable after a previous up-titration step or during the course of the 12 weeks of

treatment, dose can be reduced to the previous tolerated level or even further. Once the tolerable dose has been reached, it shall remain constant for the duration of the treatment period.

*to end of study treatment period

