3.2 Analysis Populations and Subgroups

3.2.1 Definition of Analysis Populations

Safety Analysis Set

The Safety Analysis Set consists of all subjects who received at least one dose of study drug. Subjects will be analyzed according to the treatment they actually received. The Safety Analysis Set will be the analysis set used for all safety analyses.

Intent-to-Treat Set

The Intent-to-Treat set (ITT) consists of all subjects who are randomized, whether or not study drug is received. Subjects will be analyzed according to their randomized group.

Full Analysis Set (also considered the modified Intent-to-Treat set)

The Full Analysis Set (FAS) or modified Intent-to-Treat set (mITT) consists of all randomized subjects who receive at least 1 dose of study drug, and have at least 1 efficacy evaluation after receiving study drug. Subjects will be analyzed according to their randomized group. The FAS will be the primary analysis set for efficacy analyses.

Per Protocol Set

The Per Protocol Set (PP) is a subset of the FAS that includes all subjects who complete the Week 12 visit and have no major protocol deviations that are deemed to impact efficacy. These violations include but are not limited to violations of inclusion/exclusion criteria deemed to impact efficacy, inadequate study drug compliance over the dosing period as determined from the dosing information in the eCRF, usage of prohibited concomitant medications, and incorrect randomization. Subjects will be analyzed according to their randomized treatment group. The PP set will be used for the analysis of the key efficacy endpoints only.

Prior to database lock and unblinding, there will be a meeting to review protocol deviations. The threshold for percent compliance that would be considered inadequate and would result in exclusion from the per protocol set will be determined in this meeting following review of the relevant compliance information. In addition to the deviations listed above, other relevant protocol deviations, like early termination of treatment, may be identified for review.

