3.10 Interim Analysis

3.11 Changes from Protocol

Description of Caregiver:

During development of the study eCRFs, the relationship of the caregiver to the subject was collected in order to identify type of relationship as: parent, grandparent, friend, or other (like a group home resident).

Criteria for Per Protocol Determination:

Prior to database lock and unblinding, there will be a meeting to review protocol deviations. The threshold for percent treatment compliance that would be considered inadequate and would result in exclusion from the per protocol set will be determined in this meeting following review of the relevant compliance information. In the study

protocol 80% treatment compliance was specified as the threshold defining the per protocol exclusion, however, due to the allowance of down-titration in this study, it was determined that treatment compliance cannot be assessed with sufficient accuracy to warrant a strict 80% threshold. A lower threshold may be considered in the abovementioned meeting. If it is decided to lower the compliance threshold, this change will be documented in the CSR.

ABC-I Assessment at Clinic Visits:

The ABC-I is the irritability scale from the ABC-C. The ABC-I Completed by Clinician assessment described in the protocol consisted of the clinician completing the questionnaire based on the caregiver's response. In the protocol Schedule of

Assessments, both ABC-I Clinician and ABC-C Caregiver were noted to be completed during clinic visits. However, in practice during the study, the ABC-I Clinician assessment was often not entered during clinic visits. Since the information is captured in the ABC-C Caregiver assessment, this data will be used to supplement the ABC-I assessment if missing at clinic visits.

The hypothesized treatment effects on efficacy have shifted based on results from related studies that have been reported after the protocol was developed.

Primary Comparisons of Interest:

The protocol states that the primary comparisons of interest are between each active treatment group (dose group) and placebo group. In the SAP, it is determined that the primary comparisons of interest are between the combined OV101 group and placebo, in order to increase statistical power.

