8. Unless otherwise specified, the estimated mean and median for a set of values should be printed out to one more decimal place than the raw (observed) data and rounded appropriately. Standard errors (or standard deviations) should be printed out to two additional decimal places than the raw (observed) data and rounded appropriately. For example, for age (with raw data in whole years):

n	xx
Mean (SD)	xx.x (xx.xx)
Median	xx.x
Min, Max	xx,xx

9. The p-values will be printed in the tables rounded appropriately to 4 decimal places and formatted as '0.xxxx'. P-values less than 0.0001 will be formatted in the tables as '<0.0001'.
10. All fractional numeric values should be printed with a zero to the left of the decimal point (e.g., 0.12, 0.3).
11. Unless otherwise specified, percentage values should be printed with one digit to the right of the decimal point (e.g., 12.8%, 5.4%).
12. Missing data should be represented on subject listings as either a hyphen ("--").
13. Dates printed as a result in the table, listing, or graph should be printed in SAS DATE9. format ("DDMONYYYY": 01 JUL 2002). Missing portions of dates should be represented on subject listings as dashes (-- JUL 99). Dates that are missing because they are not applicable for the subject should be listed as "N/A", unless otherwise specified.

6 List of Tables

Table 14.1.1	Subject Disposition, All Subjects
Table 14.1.2.1	Demographics and Baseline Characteristics, Safety Set
Table 14.1.2.2	Demographics and Baseline Characteristics, Full Analysis Set
Table 14.1.2.3	Demographics and Baseline Characteristics, Per Protocol Set
Table 14.1.3.1	Medical and Surgical History, Safety Set
Table 14.1.3.2	Medical and Surgical History, Full Analysis Set
Table 14.1.3.3	Medical and Surgical History, Per Protocol Set
Table 14.1.4	Prior Medications, Safety Set
Table 14.1.5	Concomitant Medications, Safety Set
Table 14.1.6.1	Study Drug Exposure, Safety Set
Table 14.1.6.2	Study Drug Exposure, Full Analysis Set
Table 14.1.7.1	Study Drug Compliance, Safety Set
Table 14.1.7.2	Study Drug Compliance, Full Analysis Set
Table 14.2.1.1.1	Response Based on Clinical Global Impressions – Improvement (CGI-I) as Assessed by Clinician at Week 12 Comparing OV101 and Placebo, Full Analysis Set
Table 14.2.1.1.2	Response Based on Clinical Global Impressions – Improvement (CGI-I) as Assessed by Clinician at Week 12 Comparing OV101 and Placebo, Per Protocol Set

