10.1.3.2 Treatment Period (12 Weeks)

Baseline Visit (Day 1; Full Day Visit)

Eligible subjects will return to the study center for the Baseline (Day 1) visit. Caregivers will bring the e-Diary and wearables. Prior to randomization, study center staff must confirm proper recording of the wearables, appropriate completion of the e-Diary, and fulfillment of all selection criteria.

Subjects will be randomized on a 1:1:1 ratio according to the following dosing schedule:

- Schedule A: a single evening dose of OV101 (QD) plus morning placebo
- Schedule B: a morning plus evening dose of OV101 (BID)
- Schedule C: morning and evening placebo

- Subjects will receive the assigned package of blinded study treatment as per treatment code for the titration period and until the next scheduled visit at Week 6
- Baseline safety and efficacy assessments will be conducted

- Baseline laboratory assessments will be performed

The e-Diary will be kept by the caregiver throughout the study. It must be charged overnight each day by the caregiver. Study center staff shall remotely check data completeness at least once a week and contact caregiver if there is non-adherence, such as missing data.

Titration (Day 1 to Day 14)

Section 12.1.1 details the dosing schedule.

During the titration period (Day 1 to Day 14), doses progressively increase in 5 mg increments according to the titration schedule, allowing slower up- or down-titration if the OV101 or placebo treatment is not tolerated (Table 2) up to a target evening dose of 15 mg (3 capsules) in Schedules A and B, and up to a target morning dose of 10 mg (2 capsules) in Schedule B. Multiple phone visits are scheduled to confirm tolerability of study treatment. Each dose-escalation will be performed after adequate tolerability has been assessed by the caregiver and investigator during a phone visit. At any time, ad-hoc study center visits may occur to further assess drug safety. These should follow the script for phone visits.

If the target dose is not achieved at Day 14 (due to slowed titration based on intolerance), the up-titration can continue until the target dose or the maximum tolerated dose is reached. Additional phone visits to agree on next titration level will be performed. As a general guidance for investigators, for subjects undergoing a slowed titration regimen, the maximal tolerated dose for the duration of the study should be reached by Day 21.

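### SAP % Compliance divides by the planned full-target titration, not the capsules prescribed, so full adherence to a permitted, sustained lower dose scores as non-compliance

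*SAP*

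**What the plan says.** SAP 3.7.1 defines % Compliance as capsules taken over a denominator that depends only on DAYS (last dose date minus first dose date plus 1). It explains that "The formula for % Compliance is based on the planned titration schedule". From Day 14 on, the denominator is 5 x (DAYS - 13) + 35.

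The same documents allow lower doses. SAP 2.2 says that, if tolerability is not acceptable, the "dose can be reduced to the previous tolerated level or even further". SAP 2.2 and protocol 12.1.3.6 then have the tolerated dose held for the rest of treatment. Protocol 12.1.3.5 allows delayed up-titration, and protocol 10.1.3.2 adds as guidance that "for subjects undergoing a slowed titration regimen, the maximal tolerated dose for the duration of the study should be reached by Day 21".

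Protocol 17.2.2 lists compliance below 80% as a ground for exclusion from the Per Protocol Set. SAP 3.2.1 leaves open "The threshold for percent compliance that would be considered inadequate and would result in exclusion from the per protocol set", to be settled at a meeting before database lock and unblinding. SAP 3.11 gives the reason: "due to the allowance of down-titration in this study, it was determined that treatment compliance cannot be assessed with sufficient accuracy" to justify a strict 80%. It continues: "A lower threshold may be considered in the abovementioned meeting". The formula in 3.7.1 is not changed. Its values go into Table 14.1.7.1 ("Study Drug Compliance, Safety Set") and Table 14.1.7.2 (the same for the Full Analysis Set).

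**The concern.** The index mixes two things: how much of the prescribed treatment the subject took, and how far the prescribed dose lay below target. A subject who follows the investigator's instructions exactly on a reduced dose gets a low value that is reported as compliance.

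Two outputs depend on this. Tables 14.1.7.1 and 14.1.7.2 will not show adherence for subjects on a sustained reduction. And the Per Protocol exclusion is framed as a threshold on percent compliance, with no written rule for an adherent subject on a reduced dose. Moving the threshold cannot repair this, because subjects with very different adherence can have the same score.

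**Working it through.** **Inputs.** Planned capsules per day, from the titration steps in protocol 12.1.3.3-12.1.3.4: 1 on Days 1-2, 2 on Days 3-6, 3 on Days 7-9, 4 on Days 10-13, 5 from Day 14 (3 evening plus 2 morning). Formula from SAP 3.7.1. The dose paths below are illustrative.

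**The SAP's own examples.** 2 days, 1 capsule: 100 x 1/2 = 50%. 21 days, 60 capsules: denominator (21 - 13) x 5 + 35 = 75, and 100 x 60/75 = 80%. Both reproduce. The denominator equals the running sum of planned capsules for every DAYS from 1 to 99, so the arithmetic is right. The issue is what it divides by.

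**Denominator at DAYS = 84.** (84 - 13) x 5 + 35 = 390.

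**Subjects who take every prescribed capsule, DAYS = 84:**

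| Path | Capsules taken | Score |
|---|---|---|
| Ceiling of 3, evening only | 2x1 + 4x2 + 78x3 = 244 | 62.6% |
| Ceiling of 2, evening only | 2x1 + 82x2 = 166 | 42.6% |
| Ceiling of 4 | 19 + 75x4 = 319 | 81.8% |
| Target on Day 14, then 4 from Day 15 | 35 + 5 + 70x4 = 320 | 82.1% |
| Same, without the Day 84 evening dose (3 capsules) | 317 | 81.3% |
| Slowed, target reached on Day 21 | 6x1 + 3x2 + 4x3 + 7x4 + 64x5 = 372 | 95.4% |

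If an evening-only subject takes the last dose on the evening of Day 83, DAYS is 83 and the denominator is 70 x 5 + 35 = 385. The scores are 241/385 = 62.6% and 164/385 = 42.6%, unchanged to one decimal.

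**Reduction from 5 to 3 a day, starting on day s, against the protocol's 80%.**
- DAYS = 84: 80% of 390 is 312. 390 - 2 x (85 - s) < 312 gives s <= 45.
- DAYS = 87 (end of the visit window, denominator 405, 80% is 324): 405 - 2 x (88 - s) < 324 gives s <= 47.
- DAYS = 87, reduced dose of 2 evening plus 1 morning, no evening dose on the last day: 403 - 2 x (88 - s) < 324 gives s <= 48.

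The latest start that falls below 80% is therefore Day 45-48, depending on visit timing and the morning/evening split (45-47 for an evening-only reduced dose).

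**Tied scores.** A full-target subject who misses 146 of 390 capsules (37.4%) takes 244 and scores 62.6%, exactly as the adherent subject at 3 a day does. A cut-off of 62% keeps both; 63% excludes both. With prescribed capsules as the denominator, they score 244/244 = 100% and 244/390 = 62.6%.

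**Wrong ordering.** A subject at 3 a day who takes 195 of 244 prescribed capsules (79.9%) scores 195/390 = 50.0%, below the full-target subject who missed 37.4%.

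**The case against.** The strongest reply is that SAP 3.11 already deals with this. It names down-titration as the cause, declares the departure from 80%, and places the decision before unblinding. SAP 3.2.1 does not tie the meeting to the formula: it speaks of dosing information in the eCRF and of reviewing relevant compliance information, so the meeting may treat an adherent reduced-dose subject sensibly. All of that stands. What remains is that the only remedy named is a lower threshold, which cannot separate tied scores, and that no meeting decision corrects the compliance tables.

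It can also be said that the SAP openly calls the index relative to the planned schedule, and that exposure has its own tables (14.1.6.1 and 14.1.6.2). True, but the values are still labelled compliance and still feed a compliance exclusion.

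Materiality is limited, and this also stands. For the Per Protocol Set, "The PP set will be used for the analysis of the key efficacy endpoints only". Safety uses the Safety Analysis Set, and the FAS is primary for efficacy.

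Three stronger readings are tempting but not supported:
- A reader might infer that adherent subjects will be wrongly excluded, mostly from the OV101 arms. Reductions follow intolerance, so an imbalance is possible. But the documents give no reduction rate, and the SAP has not fixed a threshold; the 80% crossings above refer to a cut-off it no longer holds itself to.
- A reader might infer that slowed titration as such breaks the index. If target is still reached by Day 21, the score is about 95%.
- A reader might infer that any reduction fails 80%. A ceiling of 4 a day, or a step from 5 to 4 after reaching target, stays above it. A subject who reaches only 4 a day, and late, can fall just under: 3 a day to Day 20, then 4, gives 2 + 8 + 14x3 + 64x4 = 308, or 308/390 = 79.0%. That is a lasting lower dose, not merely a delay.

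**Conclusion.** Wrong as written, of low to moderate severity. A stated formula gives a wrong adherence value for subjects on a sustained, permitted lower dose: 62.6% or 42.6% for perfect adherence at 3 or 2 evening capsules, the first tied with a subject who missed 37.4% of a full-target prescription. The size rests on DAYS = 84 and on illustrative dose paths.

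The effect is confined to sustained or larger reductions and to two places: Tables 14.1.7.1-14.1.7.2 and membership of the Per Protocol Set. With about 25 subjects per arm, each misclassified subject would be about 1/25 = 4% of an arm in the Per Protocol analysis. How many there would be, and whether the arms would differ, cannot be derived from the documents. The FAS efficacy and safety analyses do not depend on the index.

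**What to change.** In SAP 3.7.1, define % Compliance = 100 x capsules taken / capsules prescribed. Capsules prescribed is the sum, day by day from first to last dose date, of the morning and evening capsules prescribed according to the titration steps in the eCRF; on the last day, count only the doses due.

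Query incomplete titration entries against source documents and the written dosing instructions. Flag subjects who remain unresolved for the blinded meeting rather than imputing.

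Fix one Per Protocol threshold on this measure before lock and unblinding. The protocol's 80% could be used if the titration records are complete, since down-titration would then no longer be a reason against it. The planned-schedule ratio may be kept, under the name of a relative-dose or exposure measure.

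The inputs are already planned: protocol 12.1.3.1 requires each titration step in the eCRF, and protocol 12.5 requires separate bottle counts and the reasons for leftover capsules, including physician-advised down-titration. The cost is SAP wording, one derived variable and modest programming. The weak point is reliance on complete, dated titration entries; the eCRF itself is not among the documents. No dosing rule changes.
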